12.4 Endpoints

12.4.1 Primary Endpoint

The primary end point is the subject's clinical status at Day 7 (6-point ordinal scale):

1. Death
2. In ICU
3. Non-ICU hospitalization, requiring supplemental oxygen
4. Non-ICU hospitalization, not requiring supplemental oxygen
5. Not hospitalized, but unable to resume normal activities
6. Not hospitalized with full resumption of normal activities

12.4.2 Secondary Endpoints

- Ordinal outcome assessed at Days 1, 2, 3, 7, 14, and 28
- Date of hospital admission and discharge
- Date and cause of death (if applicable)
- NEW/PEW score at Day 0, 3, and 7
- Date/time of supplemental oxygen initiation and discontinuation (if applicable)
- Date/time of ICU admission and discharge (if applicable)
- Date/time of mechanical ventilation initiation and discontinuation (if applicable)
- Date/time of meeting ARDS criteria, date of resolution, and severity (if applicable)
- Date/time of ECMO initiation and discontinuation (if applicable)
- SOFA score for age \geq 18 years and PELOD score for age $<$ 18 years on Days 0, 3, and 7
- Disposition (home, rehabilitation, chronic nursing facility) following the initial hospitalization
- Quantitative PCR for influenza in oral swab on Day 0 and 3.
- Grade 3 and 4 adverse events
- SAEs
- Safety laboratory tests will be collected on Days 0, 1, 3, and 7
- CBC with differential white cell count (to include neutrophil and lymphocyte percentages), hemoglobin, hematocrit, and platelets
- Blood chemistries (creatinine, glucose, total protein, ALT/GPT, AST/GOT, total bilirubin)
 - Hemagglutination Inhibition (HAI) titer Days 0, 1, 3, 7
 - Grade 3 and grade 4 adverse events (AEs)
 - Serious adverse events (SAEs)

13 ETHICS/PROTECTION OF HUMAN SUBJECTS

13.1 IRB/IEC Approval

This protocol, informed consent document, relevant supporting information, and all types of subject recruitment or advertisement information must be submitted to the IRB/IEC for review and must be approved before the study is initiated.

Any amendments must also be approved by the IRB/IEC prior to implementing changes in the study.

The site investigator is responsible for keeping the IRB/IEC apprised of the progress of the study as deemed appropriate, but in any case at least once a year. The site investigator must also keep the IRB/IEC informed of any significant AEs.

13.2 Compliance with Good Clinical Practices (GCP)

This study will be conducted in compliance with the conditions stipulated by NIAID and local IRB/IEC, informed consent regulations, U.S. FDA regulations, and ICH/GCP Guidelines. In addition, all local regulatory requirements will be adhered to, in particular those which afford greater protection to the safety of the trial participants.

13.3 Informed Consent

The informed consent form for this study must be signed by the study subject or legal representative before participation in the study. A copy of the signed consent must be provided to the study subject. Signed consents must remain in each study subject's study file and be available for verification by study monitors at any time.

In the case of illiterate subjects, the consent form can be read to the subjects. IRB approval for use of the oral consent process will be obtained if required by the policy at the individual site.

If the subject is too ill to consent, the Legally Authorized Representative may consent for the subject. Once the subject is able, the subject will be consented for continuation in the study.

13.4 Rationale for Research Subject Selection

13.4.1 Inclusion of Children

Children represent a significant portion of those infected with influenza, and children can develop severe influenza. The optimal treatment of these children is not clear, and significant morbidity and mortality exist despite treatment with antivirals. Furthermore, standard plasma is frequently used in a critically ill pediatric population.

The close monitoring of subjects in this study will allow for early detection of complications from influenza, and therefore contributing to the subject's well-being (45 CFR 46.405). Additionally, this research study presents a reasonable opportunity to further the understanding of the treatment of severe influenza, which is a serious problem affecting the health or welfare of children (45 CFR 46.406). For these reasons children are eligible for enrollment into this protocol.

13.4.2 Inclusion of Pregnant Women

Pregnant women represent a significant portion of those infected with influenza. The optimal treatment of this group is also not clear, and significant morbidity and mortality exist despite treatment with antivirals. Furthermore, standard plasma is frequently used in a critically ill pregnant population. All study plasma has tested negative for Zika Virus (as well as other pathogens as previously described in Section 5.1). For these reasons, pregnant women are eligible for enrollment into this protocol.

13.4.3 Inclusion of Subjects Unable to Provide Informed Consent

While there are some risks associated with the plasma, given the potential for direct benefits of anti-influenza plasma to the individual subjects (as suggested by the previous study of anti-influenza plasma), participation in the study is allowed for subjects unable to provide informed consent.

13.4.4 Justification of Exclusions

The exclusion criteria are primarily to increase subject safety.

13.5 Anonymity and Confidentiality

The information obtained during the conduct of this clinical study is confidential. The results of the research study may be published, but subject names or identities will not be revealed. Records will remain confidential. To maintain confidentiality, the site investigators will keep records in locked cabinets and the results of tests will be coded to prevent association with the subject's names.

13.6 Compensation

Each site is responsible for generating a compensation scheme accounting for travel cost and time lost from work for outpatient visits, and that fits the local legal and regulatory requirements as well as the cultural norm.

14 DATA MANAGEMENT AND MONITORING

14.1 Source Documents

The primary source documents for this study will be the subjects' medical records. If the investigators maintain separate research records, both the medical record and the research records will be considered the source documents for the purposes of auditing the study. The investigator will retain a copy of source documents. The investigator will permit monitoring and auditing of these data, and will allow NIAID, SSS, IRB/IEC, and regulatory authorities access to the original source documents, regardless of media.

The investigator is responsible for ensuring that the data collected are complete, accurate, and recorded in a timely manner. Source documentation (the point of initial recording of information) should support the data collected and entered in to the study database and must be signed and dated by the person recording and/or reviewing the data. All data submitted should be reviewed by the site investigator and signed as required with written or electronic signature, as appropriate. Data entered into the study database will be collected directly from subjects during study visits or will be abstracted from subjects' medical records. The subjects' medical records must record their participation in the clinical trial and what medications (with doses and frequency) or other medical interventions or treatments were administered, as well as any AEs experienced during the trial.

14.2 Data Management Plan

Study data will be collected at the study site(s) and entered into the study database. Data entry is to be completed on an ongoing basis during the study.

14.3 Data Capture Methods

Clinical data will be entered into a 21 CFR 11-compliant Internet Data Entry System (IDES). The data system includes password protection and internal quality checks to identify data that appear inconsistent, incomplete, or inaccurate.

14.4 Study Record Retention

The site investigator is responsible for retaining all essential documents listed in the ICH GCP Guidelines. The FDA requires study records to be retained for up to 2 years after marketing approval or disapproval (21 CFR 312.62), or until at least 2 years have elapsed since the formal discontinuation of clinical development of the investigational agent for a specific indication. These records are also to be maintained in compliance with IRB/IEC, state, and federal medical records retention requirements, whichever is longest. All stored records are to be kept confidential to the extent provided by federal, state, and local law. It is the site investigator's responsibility to retain copies of source documents until receipt of written notification to the contrary from OCRPRO/DCR/NIAID. No study document should be destroyed without prior written agreement between OCRPRO/DCR/NIAID and the Principal Investigator.

Should the investigator wish to assign the study records to another party and/or move them to another location, the site investigator must provide written notification of such intent to OCRPRO/DCR/NIAID with the name of the person who will accept responsibility for the transferred records and/or their new location. NIAID must be notified in writing and written NIAID permission must be received by the site prior to destruction or relocation of research records.

16 APPENDIX A

IRC005 will use the Division of AIDS Table for Grading the Severity of Adult and Pediatric Adverse Events, Version 2.0, November 2014 to grade AEs and laboratory abnormalities.

This table can be found at: <https://nirc.s-3.com/irc005/node/1835>

**ClinicalTrials.gov Identifier: NCT02572817**

## **Introduction**

This document describes the content proposed for the final primary statistical analysis of IRC 005. The focus is on analyses that address the major randomized comparisons for key safety, tolerability and efficacy outcome measures, including those needed to address the study's primary and secondary objectives.

## Protocol Summary

Full Title:	A Randomized Double-Blind, Phase 3 Study Comparing the Efficacy and Safety of High-Titer versus Low-Titer Anti-Influenza Immune Plasma for the Treatment of Severe Influenza A
Short Title:	IRC-005
Clinical Phase:	3
IND Sponsor:	OCRPRO, NIAID
Conducted by:	NIAID Influenza Research Collaboration (NIRC)
Sample Size:	150
Accrual Ceiling:	300 subjects will be screened to randomize 150 subjects
Study Population:	Subjects aged two weeks or older, including children and pregnant women, hospitalized with severe influenza A infection
Study Duration:	November 2015 – November 2018
Study Design:	
This randomized, double-blinded, multicenter phase 3 trial will assess the efficacy and safety of anti-influenza immune plasma as an addition to standard of care antivirals in subjects hospitalized with severe influenza A infection (as defined in the inclusion criteria). Up to 40 sites in the United States will participate in this protocol. Adults and children may participate. There is no exclusion for pregnancy. A total of 150 eligible subjects will be randomized in a 2:1 ratio to receive either high-titer anti-influenza plasma or control (low-titer) plasma. All subjects will receive standard care antivirals. Randomization will be stratified by:
 

• severity: in the intensive care unit (ICU), non-ICU hospitalization requiring supplemental oxygen, or non-ICU hospitalization not requiring supplemental oxygen

• age category (child/adult).

	
Subjects will be assessed on Day 0 (baseline) and on Days 1, 2, 3, 7, 14, and 28. For subjects who are not hospitalized on Days 2, 14, and 28, contact with the subject for the purpose of study data collection on those days may be performed by telephone.

	
All subjects will undergo a series of efficacy, safety, and hemagglutination inhibition (HAI) assessments during the study. Blood samples will be collected on Day 0, 1, 3, and 7. Oropharyngeal (OP) swabs for influenza PCR will be obtained on Days 0 and 3.

**Study Agent:** All plasma is from male donors to minimize the risk of transfusion-related acute lung injury (TRALI). The high-titer arm will receive 2 units of human plasma (FFP or FP24, 250-350 mL per unit, or pediatric equivalent) with influenza A/H1N1 and A/H3N2 HAI titers of at least 1:80. The sponsor will try to supply units with as high a HAI as possible. The antigens for the HAI will be for Protocol IRC005 contemporary strains defined as strains contained within that year's seasonal trivalent influenza vaccine.

The control (low-titer) arm will receive 2 units of human plasma (FFP or FP24, 250-350 mL or pediatric equivalent) with influenza A/H1N1 and A/H3N2 HAI titers of 1:10 or less.

**Primary Objective:** Evaluate the efficacy of treatment with high-titer versus low-titer anti-influenza immune plasma as an addition to standard care in subjects hospitalized with severe influenza A by clinical status at Day 7.

**Primary Endpoint:** Subjects clinical status at Day 7 (6-point ordinal scale):

1. death;
2. in ICU;
3. non-ICU hospitalization, requiring supplemental oxygen;
4. non-ICU hospitalization, not requiring supplemental oxygen;
5. not hospitalized, but unable to resume normal activities; or
6. not hospitalized with full resumption of normal activities.

**Secondary Objectives:**

1. Evaluate the efficacy and safety of treatment with high-titer versus low-titer anti-influenza immune plasma plus standard care, using the following parameters:
  - Subject clinical status (6-point ordinal scale) at Days 1, 2, 3, 14, and 28
  - Duration of initial hospitalization
  - 28-day mortality
  - In-hospital mortality during initial hospitalization
  - Composite of mortality and hospitalization at Days 7, 14, and 28
  - Change from baseline to Day 3 and Day 7 in National Early Warning (NEW) score
  - Duration of supplemental oxygen use among those requiring oxygen at randomization
  - Incidence of new oxygen use during the study
  - Duration of ICU stay among those requiring ICU admission at randomization
  - Incidence of new ICU admission during the study
  - Duration of mechanical ventilation use among those requiring mechanical ventilation at randomization
  - Incidence of new mechanical ventilation use during the study
  - Duration and severity of acute respiratory distress syndrome (ARDS) among those meeting definition of ARDS at randomization

- Incidence and severity of new ARDS during the study
- Duration of extra corporeal membrane oxygenation (ECMO) use among those requiring ECMO at randomization
- Incidence of new ECMO use during the study
- Change from baseline to Day 3 and Day 7 in sequential organ failure assessment (SOFA) score for age  $\geq 18$  years, and pediatric logistic organ dysfunction (PELOD) score for age  $< 18$  years
- Disposition (home, rehabilitation, chronic nursing facility, initial hospitalization ongoing at 28 days, died in hospital) following the initial hospitalization
- Percent of subjects with influenza virus detectable in OP sample at Day 3

2. Compare the plasma and control groups for HAI titers at Days 1, 3, and 7.
3. Evaluate the safety of high titer anti-influenza plasma as compared to low titer plasma as assessed by:
  - Cumulative incidence of grade 3 and grade 4 adverse events (AEs)
  - Cumulative incidence of serious adverse events (SAEs)

## **1. General analysis considerations**

Unless otherwise specified, data summaries and analyses will be presented overall and by randomized arm. For tables with categorical variables, the number (%) will be presented. For tables with continuous variables, the mean, standard deviation, median, 25th and 75th percentiles, min and max will be presented. The number with missing values will also be shown. In calculation of percentages, subjects with missing data will not be included in the denominator.

Unless otherwise stated, analyses will be restricted to subjects with non-missing data or available follow-up time for the endpoint of interest. Tables/figures will show the number of subjects included in the analysis. Sensitivity analyses may be undertaken using (1) the last available measurement carried forward, and (2) extreme scenarios in which subjects are assigned in the worst status in one randomized arm and the best in the other (and vice versa) to illustrate the sensitivity of conclusions to any incompleteness in the data.

Appendices to the report will provide tables and figures for adults (age  $\geq 18$  years) and children (age  $< 18$  years) separately.

To help protect participant confidentiality, listings of individual patient level data will be minimized as much as possible. Dates will also not be presented in listings; instead, for example, listings will present details as days since randomization.

## **2. Application validation**

All study-specific programs for creation of derived datasets defined in this document will require application validation and verification per written Standard Operating Procedures as appropriate.

## **3. Visit and Evaluation Schedule**

The expected schedule for clinic visits (per protocol) is shown in **Table 1** below. The visit windows are often small with the goal of better data. Visits outside these windows are considered deviations. However, to allow use of data collected outside these windows, the visit windows have been expanded for analysis purposes as indicated. If there are multiple measurements within a window, then the one closest to the scheduled time will be used in analysis.

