4.4 Subject Withdrawal

Subjects (or their legal surrogates if subjects are or become unable to make informed decisions) can terminate study participation at any time without prejudice. Subjects who indicate interest in withdrawing from the study should be asked about possible limited further study data collection and/or data usage, rather than full withdrawal. The most important data to obtain is safety data through Day 28 and primary endpoint data (clinical status at Day 7). This would require, at a minimum, a Day 28 by telephone contact for vital status (date of discharge, disposition, and any adverse events that occurred during the study) and a review of the available subject information for clinical status at Day 7. This is not considered full withdrawal of consent. The modified consent for limited follow-up should be noted in the source documentation.

Subjects who fully withdraw consent will not be contacted further. The reason for withdrawal from the study is to be recorded in the source records and eCRF.

Randomized subjects who withdraw from the study will not be replaced.

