6 STUDY PROCEDURES

6.1 Schedule of Evaluations

A schedule of evaluations is presented as Table 5. A detailed presentation of assessments immediately follows the table. To ensure similar assessments of efficacy after plasma administration, the day of randomization will be noted to be Study Day 0, the first day after randomization is Study Day 1, etc. If the plasma is not administered until the day after randomization, the day of randomization should still be noted to be Study Day 0.

In an attempt to standardize the data, the follow up study visits should preferably occur in the morning (i.e. prior to noon). However, any visit within the window (as defined on the schedule of evaluations is acceptable).

Table 5: Schedule of Evaluations

| | Screen | Base line | Randomization | Study Plasma Administration | | | Follow-up | | | | | |
|--|-----------------------|------------------|----------------------|------------------------------------|------------------------|-------------------------------------|------------------|-----------|----------|--------------|----------------|----------------|
| | Day +/- Window | -1 to 0 | 0 | 0 | | | 1 | 2* | 3 | 7 ± 1 | 14 ± 2* | 28 + 4* |
| Evaluation/Procedure | | | | Pre-infusion | 1st unit plasma | 2nd unit plasma)⁵ | | | | | | |
| ELIGIBILITY | | | | | | | | | | | | |
| Informed consent | | X | | | | | | | | | | |
| Demographics & Medical History | | X | | | | | | | | | | |
| Influenza A testing (PCR or rapid Ag) ¹ | | X | | | | | | | | | | |
| ABO typing ² | | X | | | | | | | | | | |
| STUDY DRUG ADMINISTRATION | | | | | | | | | | | | |
| Randomize subject | | | | X | | | | | | | | |
| Plasma infusion | | | | | | X | X | | | | | |
| STUDY PROCEDURES | | | | | | | | | | | | |
| Vital signs including SpO ₂ | X | X | | X | X | X | X | X | X | X | X | X |
| Clinical Data ³ | X | X | | | | | X | X | X | X | X | X |
| Concomitant medications | | X | | X | | | X | X | X | X | X | X |
| Adverse events | | X | | | X | X | X | X | X | X | X | X |
| SAFETY LABORATORY | | | | | | | | | | | | |
| CBC, Chemistry Panel, and PT/INR ⁴ | | X | | | | | X | | X | X | | |
| Pregnancy test (for females of childbearing potential) | | X | | | | | | | | | | |
| RESEARCH LABORATORY PROCEDURES | | | | | | | | | | | | |
| Blood for Serum | | | X | | | | | X | | X | X | |
| Oropharyngeal Swab for virus isolation | | | X | | | | | | X | | | |

Notes:

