6.3.8.4 Day 7 Clinical Status

If the Day 7 visit does not occur, in person, attempts should be made to call the subject to obtain information about their disposition and functional status (in order to score the Day 7 Clinical Status [primary endpoint]). If the subject cannot be reached by phone, the hospital record should be reviewed to determine if/when the subject was discharged, and to determine the clinical status on Day 7. This missed visit may still be a protocol deviation, but this would allow the primary endpoint to be ascertained.

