7.3 Efficacy Measures

7.3.1 Ordinal Scale

The ordinal scale is an assessment of the clinical status at the first assessment of a given study day (i.e., at approximately 8AM). The clinical status should be recorded as the subject currently exists, without consideration as to need (i.e., is the subject in the ICU, and not does the subject have medical needs to be in the ICU, or has the subject been discharged home and not is the subject capable at that moment of being discharged to home). The scale is as follows:

1. Death
2. In ICU
3. Non-ICU hospitalization, requiring supplemental oxygen
4. Non-ICU hospitalization, not requiring supplemental oxygen

5. Not hospitalized, but unable to resume normal activities
6. Not hospitalized with full resumption of normal activities

For the purposes of this study, resumption of normal activities refers to resumption of activities that the subject could undertake prior to first onset of symptom(s) of influenza.

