7.3.7 Measures of clinical support

At each study day, the following measure of clinical support should be assessed:

- Hospitalization
- Oxygen requirement
- Mechanical ventilator requirement
- ICU requirement
- ECMO requirement

If any of these are present, it should be determined if these are new or ongoing from previous study visits. In the case of a new requirement, the date started should be recorded (not just the date of assessment).

If there were previous interventions that are no longer needed, the date of discontinuation should be noted (not just the date of assessment).

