**Table 1. IRC005 study days and analysis windows**

	Days since randomization						
Visit	Day 0 (Baseline)	Day 1	Day 2	Day 3	Day 7	Day 14	Day 28
Per protocol (Days)	0	1	2	3	7±1	14±2	28±3
Analysis (Days)	0	1	2	3-4	5-9	10-18	22-36

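### Minor: the SAP lets a lone Day 5 or Day 9 record stand as the primary Day 7 status, although dates already collected could usually place the subject on Day 7

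*SAP*

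**What the plan says.** - **Windows.** SAP section 3 states that "to allow use of data collected outside these windows, the visit windows have been expanded for analysis purposes as indicated". Its Table 1, "IRC005 study days and analysis windows", gives Day 7 as 7±1 per protocol and 5–9 for analysis. If a window holds several measurements, the one closest to the scheduled time is used. SAP 10.1 sets no separate rule for the primary endpoint.
- **Protocol tolerance.** Protocol 6.1 says "any visit within the window (as defined on the schedule of evaluations is acceptable", so assessments on Days 6 and 8 comply with the protocol.
- **What is measured.** Protocol 7.3.1: "The ordinal scale is an assessment of the clinical status at the first assessment of a given study day (i.e., at approximately 8AM".
- **Missed visits.** Protocol 6.3.8.4 asks sites to telephone. If that fails, "the hospital record should be reviewed to determine if/when the subject was discharged, and to determine the clinical status on Day 7". For subjects who agree to limited follow-up, Protocol 4.4 asks for "a review of the available subject information for clinical status at Day 7".
- **Dates.** For a new support requirement, Protocol 7.3.7 says "the date started should be recorded (not just the date of assessment"; stop dates are recorded too. Protocol 12.4.2 lists "Date of hospital admission and discharge", the date of death, and date/times for ICU stay and oxygen use.
- **Missing data.** SAP 10.1 plans a sensitivity analysis using last known status. SAP section 1 allows optional best/worst scenarios.

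**The concern.** The endpoint is clinical status on a particular morning. Under the closest-record rule, a subject with only a Day 9 record is given the Day 9 state. A discharge or death after Day 7 is then scored as if it had happened by Day 7. A lone Day 5 record errs the other way: a subject still in hospital on Day 5 who goes home on Day 6 is scored as in hospital.

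The planned sensitivity analyses do not reveal this, because a Day 5 or Day 9 record counts as observed and not as missing. Nor does any planned table show how many primary-endpoint records fall off Day 7. The SAP does not say that a status established for Day 7 under Protocol 6.3.8.4 or 4.4 outranks an off-day record. It also does not tie the Day 7 composite in SAP 10.2b to the same derivation, so one subject could be classed differently in the two analyses.

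By contrast, SAP 8.1c sets a date/time cut-off for Day 28 mortality and requires agreement with the ordinal record.

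**Working it through.** **1. The plan's own power.** Inputs from Protocol 12.2: 135 effective subjects, 2:1 allocation, two-sided 0.05, odds ratio 2.50, and the Table 12 distributions. For a proportional odds analysis, V = N·a(1−a)/3·(1 − Σp̄³), where a = 2/3 and p̄ is the allocation-weighted mean proportion in each category.
- p̄ = 6.2, 25.3, 24.1, 12.2, 6.9 and 25.4%, so Σp̄³ ≈ 0.049.
- V = 135 × (2/9)/3 × 0.951 = 9.51.
- Power = Φ(ln 2.50 × √9.51 − 1.96) = Φ(0.866) = 80.7%.

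The stated 80% reproduces. Simulation with the score (Wilcoxon) test, 90 versus 45 subjects, gives 79.65%, which is the base used below.

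**2. Which days the SAP adds.** Days 5–9 less Days 6–8 leaves Days 5 and 9.

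**3. How often two days matter.** In IRC002, Protocol Table 1 puts the first quartile and median of hospital days at 4 and 9, so about 25% had left hospital or died by Day 4 and 50% by Day 9. Protocol Table 3 gives (25 + 6 + 5)/87 = 41.4% at Day 7.
- Slopes: (41.4 − 25)/3 = 5.5 and (50 − 41.4)/2 = 4.3 points per day, so 8.6–11.0 points over two days. This is rough, because Table 1 days include deaths and readmissions.
- If 2%, 5% or 10% of 135 (2.7, 6.75 or 13.5 subjects) have only a Day 5 or 9 record, then 0.2–0.3, 0.6–0.7 or 1.2–1.5 subjects fall on the wrong side of hospitalized versus not.

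**4. Effect on power.** Simulation as in step 1, 2,000,000 trials per scenario. Of the off-day records, 20% or 40% move one category, up or down with equal chance. Deaths do not move, and moves beyond category 2 or 6 stay put.

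| Share on Day 5 or 9 (assumed) | Power, 20% moved | Power, 40% moved | Loss from 79.65% |
|---|---|---|---|
| 2% | 79.64% | 79.59% | 0.0–0.1 |
| 5% | 79.53% | 79.38% | 0.1–0.3 |
| 10% | 79.37% | 79.09% | 0.3–0.6 |

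If moved records in categories 2 and 6 always move inward, the loss is 0.2–0.4 points at 5% and 0.4–1.0 at 10%. Type I error stays at 4.95–4.99%.

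**5. A deliberately lopsided case.** Suppose there is no true effect, 40% of off-day records are one category off, every such control is scored worse and every such high-titer subject better. The false odds ratio is then 1.04 at a 5% off-day share and 1.07 at 10%.

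**6. What the dates settle**, when they reach Day 7:
- Death: by date.
- ICU: by date/time.
- Oxygen (category 3 versus 4): by date/time.
- In hospital or not: by date.
- Category 5 versus 6: not settled; this needs a contact.

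Death and discharge carry no clock time, while the scale is read at about 8 AM. Events dated Day 7 itself therefore need a convention.

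**The case against.** Taking the closest record in a pre-specified window that is the same for both arms of a blinded trial is an ordinary way to limit missing data. The protocol also deals with most cases at the site: where discharge, ICU and oxygen information runs to Day 7, the record review in 6.3.8.4 should already yield a Day 7 status. Both points stand, and they are why this is minor.

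The calculation has a limit as well. SAP 10.1 takes the primary p-value from the Wald test and keeps the score test for sensitivity. On 40,000 shared simulated trials, power was 79.8% (Wald) and 79.3% (score), a gap as large as most of the losses in the table. The size is therefore an order of magnitude.

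Four stronger readings are tempting but not supported.
- **That the window biases the trial.** Nothing in the documents suggests that off-day records differ by arm, and even the lopsided case gives odds ratios near 1.
- **That Day 6 and Day 8 assessments should be replaced as well.** The protocol accepts them, and a direct assessment should not give way to a reconstruction.
- **That dates fix categories 1–4 outright.** Same-day events are ambiguous, and the documents do not say that every oxygen episode between visits is captured.
- **That subjects known to be out of hospital but without a contact must default to category 5 in the main analysis.** Table 12 implies 90 × 38.5% + 45 × 20% ≈ 44 such discharged subjects. Dropping 5, 10 or 20% of them from 135 gives 78.7, 77.6 or 75.6% power, but that charges the loss after the 10% allowance in Protocol 12.2 is spent. Starting from 150 (83.7%), power is about 83, 82 or 80%. The allowance is shared with other losses, yet the case for a main-analysis default is not made.

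**Conclusion.** The gap is real and minor. The SAP's rule can assign a status that was not the subject's on Day 7, in a few residual cases, although data already collected would usually correct it. The expected loss is about 0–0.3 power points if 2–5% of records fall on Day 5 or 9, and up to about 0.6 at 10%, with type I error near 5%. These figures rest on assumed off-day shares, 20–40% of those records moving one category in either direction with equal chance, and the score test. The inward-move variant reaches 1.0 point at 10%. The reason to act is that the change is cheap, concerns the primary endpoint and removes discretion. It does not rest on a large bias.

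**What to change.** In SAP 3 and 10.1, before unblinding:

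1. A status established for Day 7 under Protocol 6.3.8.4 or 4.4 takes precedence over any off-day record.
2. Assessments on Days 6–8 stay as they are.
3. Where the window holds only a Day 5 or Day 9 record, derive death, ICU, oxygen, and hospitalized versus not as of Day 7 from the recorded dates when these reach Day 7. State a convention for events dated Day 7 without a time. Use the off-day record only to separate category 5 from 6.
4. Where the dates do not reach Day 7, keep the current Day 5–9 rule.
5. Report by arm how many primary-endpoint records fall off Day 7 and on which day, and use the same derivation for the Day 7 composite in SAP 10.2b.

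If a subject is known to be out of hospital but the record cannot separate 5 from 6, state the handling. Leaving the status missing in the main analysis fits SAP section 1; assignment to category 5 then belongs in a sensitivity analysis.

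The cost is some SAP text and programming, with no new data. The same-day convention remains a choice, and the 5-versus-6 split may still rest on a contact two days away.
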